14. DATA CONTROL AND RECORD MAINTENANCE

14.1. Investigator

The Investigator will allow monitoring related to the study, audits, CEP analysis and regulatory inspections, authorizing direct access to data and source documents.

All information will be recorded in the source documents. CRF's must be fully populated and include all required data. All CRF data must be submitted to Sponsor during the study and at the end of the study. Remote data capture (electronic data capture – EDC - e-CRF) will be used to register and transmit data electronically to Sponsor.

If any Investigator ceases to conduct the study for any reason, he/she shall notify Sponsor to discuss an acceptable storage solution. Regulatory agencies will be notified with proper documentation.

An updated statement on the Investigator's form will be on file with the Sponsor for any study staff changes reported in the current statement on the Investigator's form.

Investigators must notify the CEP of protocol violations in accordance with local and CEP regulatory requirements.

14.2. Sponsor

E-CRF data is stored in a database and processed electronically. The data are reviewed for completeness and logical coherence. Automated validation programs identify missing data, discrepant data, and other data inconsistencies. Requests for data clarification are sent to the Research Center for resolution.

# **Modification History**

Version	Version Date	Author	Description
1.0	16 MARCH 2022	[name]	ORIGINAL

# Abbreviation

Abbreviation	Specification
AE	Adverse Events
ALT	Alanine Aminotransferase
APTT	Activated Partial Thromboplastin Time
AST	Aspartate Aminotransferase
BMI	Body Mass Index
CIBIS	Clinician Interview Based Impression of Severity
CK	Creatine Kinase
CKmB	Creatine Kinase mB
CNS	Central Nervous System
СРК	Creatine phosphokinase
CRF	Case Report Form
CS	Clinically Significant
C-SSRS	Columbia Suicidal Severity Rating Scale
ECG	Electrocardiogram
eCRF	Electronic Case Report Form
FDA	Food and Drug Administration
FTA-ABS	Fluorescent Treponemal Antibody Test Absorption Test
Gamma-GT	Gamma-glutamyl transferase
HAM-D	Hamilton Depression Assessment Scale
HbsAg	Hepatitis B surface antigen
HBV	Hepatitis B Virus
HD	Huntington's disease
HDL	High Density Lipoprotein
HIV	Human Immunodeficiency
HTLV	Human T Cells of Lymphotropic Virus
ICF	Informed Consent Form
ICH	International Council for Harmonisation
IL	Interleukins
INR	International normalized ratio
ITT	Intention to Treat
LDL	Low Density Lipoprotein
MAR	Missing at Random
MCH	Mean Corpuscular Hemoglobin
MCHC	Mean Corpuscular Hemoglobin Concentration
MCV	Mean Corpuscular Volume
MI	Multiple Imputation
MMRM	Mixed Model Repeated Measures
MNAR	Missing Not At Random
MPV	Mean Platelet Volume
NCS	Non Clinically Significant

PP	Per Protocol
PT	Preferred Term
RBC	Red Blood Cell
RDW	Red Cell Distribution Width
SOC	System Organ Class
TCS	Total Chorea Score
TEAE	Treatment Emergent Adverse Event
TFC	Total Functional Capacity
TMS	Total Motor Score
TNF-α	Tumor Necrosis alpha Factor
UHDRS	Unified Huntington's Disease Rating Scale
VLDL	Very Low-Density Lipoprotein
WBC	White Blood Cell Count
β-hCG	Beta-Human Chorionic Gonadotropins

#### 1. Introduction

This statistical analysis plan was drafted for the ADORE-DH protocol for Cellavita Pesquisa Científica Ltda. In this document, the contents and methods of statistical analysis will be described in details.

This statistical analysis plan was based on protocol (version Amendment 6 dated February 23, 2021) and Case Report Form (CRF, version 03-FEB-22 20:47:51).

This statistical analysis plan reflects some changes from the statistical analysis section of the protocol as these were deemed more relevant and appropriate for analysis for this HD study based on analysis of other HD studies. The clinical study report will identify changes to planned analysis between the protocol and SAP.

### 2. Study Objective (s)

The primary objective of this clinical trial is to identify the dose of Cellavita-HD product that has the best clinical response (Total Motor Scale from UHDRS).

The secondary efficacy objectives of the study are:

- Clinical neurological evaluation throughout the study (Other domains from UHDRS and HAM-D)
- Overall assessment of Huntington's disease severity (CIBIS scale)
- BMI assessment
- Assess the incidence of suicide attempts during treatment
- Neurological evaluation by imaging

The safety objective of the study is to evaluate the incidence and classification of adverse events occurring between treatments regarding type, frequency and intensity as well as abnormalities in safety data such as ECGs, Vital Signs, Chemistry & Hematology laboratory assessments, etc.

### 3. Study Design

[figure not shown]
This study is a prospective, phase II, single-center, randomized, placebo controlled, triple-blind study evaluating two test doses vs placebo in 35 participants randomized 2:2:1 into the following treatment groups:

G1: (n = 14 participants) - Lower dose: dose of  $1 \times 10^6$  cells/by weight range per administration.

G2: (n = 14 participants) - Higher dose: dose of  $2x10^6$  cells/by weight range per administration.

G3: (n = 7 participants) - Placebo: constituted by the vehicle of the investigational product.

After a 90 days screening period, participants will be included in the study and will begin treatment and follow-up phase that will last 330 days. The total period of participation in the study will be up to 420 days from the period of uniformization of the study; that is, about 14 months approximately (See figure below). Note: Ciclo below means Cycle.

Above visits take place as indicated below (for additional details on windows around visits, see schedule of assessments)

- Visit -3 inclusion (V-3): -30 to -1 days before V-2;
- Visit -2 (V-2): up to 30 + 7 days after V-3
- Visit -1 (V-1): up to 30 + 7 days after V-2
- Visit 0 (V0): first administration of cycle 1; up to 30 days after V-1
- Visit 1 (V1): second administration of cycle 1 (30 days after Visit 0)
- Visit 2 (V2): third administration of cycle 1 (60 days after Visit 0)
- Visit 3 (V3): follow-up visit (90 days after Visit 0)
- Visit 4 (V4): first administration of cycle 2 (120 days after Visit 0)
- Visit 5 (V5): second administration of cycle 2 (150 days after Visit 0)

F-SA-06-01, Version 5.0/30 Dec 2021, SOPs Link: SOP-SA-06

- Visit 6 (V6): third administration of cycle 2 (180 days after Visit 0)
- Visit 7 (V7): follow-up visit (210 days after Visit 0)
- Visit 8 (V8): first administration of cycle 3 (240 days after Visit 0)
- Visit 9 (V9): second administration of cycle 3 (270 days after Visit 0)
- Visit 10 (V10): third administration of cycle 3 (300 days after Visit 0)
- Visit 11 (V11): follow-up visit/final visit (330 days after Visit 0)

After the 11th Visit, participants will enter an extension protocol.

Subjects will be randomized and treatment initiated at V0.

The estimated number of participants was calculated considering clinical/regulatory and non-statistical assumptions. In this way, the document Considerations for the Design of Early-Phase Clinical Trials of Cellular and Gene Therapy Products - Guidance for Industry (FDA, 2015) predicts that a smaller sample size is considered appropriate for diseases considered fatal, where a major potential benefit may warrant an unknown risk. Additionally, considering conditions provided by the FDA document such as limited capacity of the investigational product manufacturing and the relatively rare prevalence of the target disease, Sponsor suggests the sample size of 35 participants, which is considered a feasible sample size and at the same time adequate to meet the proposed objective.

# Schedule of Assessments: Framework of study activities - Inclusion and Uniformization Period

	Inclusion	Uniform	ization
Activities	V-3	V-2	V-1
Addivides	-37 to -1 days before V-	Up to 30 + 7 days after V-3	30 + 7 days after V-2
Consent form (ICF)	Х		
Evaluation of inclusion/exclusion criteria	Х	Xa	Xa
Medical evaluation: medical history, and physical examination/vital data	x	Х	Х
Demographic data (date of birth, gender and race)	×		
Confirmation or performance of laboratory diagnosis of Huntington's disease	x		
Evaluation of laboratory diagnosis of Huntington's disease, if applicable		Xp	
Blood and urine collection for laboratory inclusion tests	x		
Evaluation of laboratory blood and urine tests		X	
Pregnancy urinary test for women	X	X	Х
Blood collection for serology examination	X		
Evaluation of the serology examination		X	
ECG performance	X		
Evaluation of ECG result		X	
Performance of CNS MRI	X		
Assessment of the CNS MRI result		Х	
UHDRS Scale	Х	X	Х
CIBIS Scale	Х	Х	Х
Hamilton Depression Assessment Scale (HAM-D)	Х	X	X
(1.11.11.2)	Inclusion/uniformization	Uniform	ization
	V-3	V-2	V-1
Activities	-37 to -1 days before V-	Up to 30 + 7 days after V-3	30 + 7 days after V-2
Concomitant/prior medication registration	X	X	Х
Evaluation of adverse events	Х	Х	Х
Assessment of pregnancy risk and dispensation of contraceptive method, if applicable.	X	X	×
General guidelines	Х	Х	Х

altems "d" and "e" of the inclusion criteria will be evaluated only at the inclusion visit (V-3) due to the natural fluctuation of the disease b For participants who need to carry out the laboratory diagnosis of Huntington's disease, the test will be performed at V-3 and evaluated at V-2

Inclusion criteria Item d) Obtaining 5 points or more in the motor evaluation of the UHDRS (Unified Huntington's Disease Rating Scale) at the time of inclusion; Item e) Obtaining 8 to 11 points in the functional capacity of the UHDRS scale at the time of inclusion.

Statistical Analysis Plan Version: 1.0

Schedule of Assessments: Framework of study activities - Treatment and Follow-up Period

	0/	*	\$		×	VE	9/	2	8/	6/1	747	7440
	Start of	;	7	۸3	;	?	\$	•	2	) •	:	•
Activities	treatment - Up to 30 days after V-1	30+5 days after V0	60+5 days after V0	90+5 days after V0	120+5 days after V0	150+5 days after V0	180+5 days after V0	210+5 days after V0	240+5 days after V0	270+5 days after V0	300+5 days after V0	330+5 days after V0
	1 st adm. Cycle 1	2 nd adm. Cycle 1	3 rd adm. Cycle 1	F-up.	1 st adm. Cycle 2	2 nd adm. Cycle 2	3 rd adm. Cycle 2	F-up.	1st adm. Cycle 3	2 nd adm. Cycle 3	3 rd adm. Cycle 3	Final
Evaluation of inclusion criteria/ Exclusion (except criteria "d" and "e")	×											
Evaluation of discontinuation criteria		×	×	×	×	×	×	×	×	×	×	×
Medical evaluation: medical history and physical examination/vital data	×	×	×	×	×	×	×	×	×	×	×	×
Randomization	×											
Intravenous administration of Cellavita-HD or placebo (hospitalization for a period prior to administration and for another 06 hours)	×	×	×		Xa	Xa	Xa		Xa	Xa	×	
Blood and urine collection for laboratory tests				×				×				×
Evaluation of laboratory test results					×				×			×
Pregnancy urinary test for women	×	×	×	×	×	×	×	×	×	×	×	×
Blood collection for serology												×
Evaluation of serology result												×
ECG performance				×				×				×
Evaluation of ECG result					×				×			×
ECG monitoring	×	×	×		×	×	×		×	×	×	
70 V 3 UC 3 1 V 3 V 5 V 5 V 5 V 5 V 5 V 5 V 5 V 5 V 5	. I . d O D 1 C O	12. COD CA	l				Dog 11 of 16	7630				

F-SA-06-01, Version 5.0/30 Dec 2021, SOPs Link: SOP-SA-06

Page 12 of 26

	0 / 3	٧١	۸2	V3	۸۸	V5	9/	V7	8/	6/	V11	V11°
Activities	Start of treatment - Up to 30 days after V-1	30+5 days after V0	60+5 days after V0	90+5 days after V0	120+5 days after V0	150+5 days after V0	180+5 days after V0	210+5 days after V0	240+5 days after V0	270+5 days after V0	300+5 days after V0	330+5 days after V0
	1 st adm. Cycle 1	2 nd adm. Cycle 1	3 rd adm. Cycle 1	F-up.	1 st adm. Cycle 2	2 nd adm. Cycle 2	3 rd adm. Cycle 2	F-up.	1st adm. Cycle 3	2 nd adm. Cycle 3	3 rd adm. Cycle 3	Final
UHDRS and HAM-D scale and CIBIS	×	×	×	X	×	×	×	×	×	×	×	×
MRI for CNS evaluation												×
Evaluation of CNS MRI result												×
Concomitant medication registration	×	×	×	X	×	×	×	×	×	×	×	×
Evaluation of adverse events	×	×	×	X	×	×	×	×	×	×	×	×
Assessment of pregnancy risk and dispensation of contraceptive method, if applicable.	×	×	×	×	×	×	×	×	×	×	×	Xb
General guidelines	×	X	×	X	×	×	X	×	×	×	X	×
Dispensation from the study												×

<sup>a Hospitalization for 06 hours: all procedures provided for in the protocol should be performed at the times determined, including evaluation of vital signs, clinical examination and ECG. The length of stay can be extended at the discretion of the principal investigator.

b In this visit, because it is the last visit of the study, there will be no dispensation of contraceptive method, only assessment of the risk of pregnancy.

olf any examination performed on this visit presents any clinically significant abnormality, the research participants will be invited to perform an extraordinary visit.

#### 4. Endpoints

#### 4.1. Efficacy Endpoints

#### 4.1.1. Primary Efficacy Endpoint

The primary efficacy endpoint is rate of change (slope) per year from Baseline to V11 in total motor score (TMS) from the UHDRS.

Baseline is defined as the last non-missing value prior to first infusion at V0. If a value was not collected at V0 the nearest prior non-missing value is used as the Baseline value.

The TMS Score is the sum of the 31 items in the Motor Assessment portion of UHDRS with each item rated 0 to 4. The TMS is between 0 (Best) to 124 (Worst).

#### 4.1.2. Secondary Efficacy Endpoints

Secondary efficacy endpoints will include the following:

From UHDRS: TMS (at V7), Total Chorea Score (TCS), Total Functional Capacity (TFC), Functional Assessment (FA), Behavioral Assessment (BA), Independence Scale (IS), Cognitive assessments (CA) of (F, A and S combined, Digits Direct, Reversed and both combined and Stroop posters individually and all combined).

TCS is based on 7 items (eCRF items 12.1 through 12.7) from 12.1 Chorea (FACE) through 12.7 12.7 Chorea (LLE).

TFC is based on 5 items for a score between 0 (worst) to 13 (best).

FA is based on 25 item with Yes (1), No (0) answers to get a score between 0 (worst) to 25 (best).

BA is based on 16 items with a score of 0 (best) to 93 (worst)

IS is a single assessment with scores from 10 (worst) to 100 (best)

Cognitive scores are based on 5 items that are added up with a score from 0 to > 300 with higher scores being better. The 5 items include SDMT, SWR.

In addition to the above scores derived from the UHDRS the following additional secondary endpoints will be derived:

CIBIS from 1 (Normal) to 7 (Among the most extremely ill patients). 0 is not assessed and will not be summed.

Body Mass Index (BMI) (Kg/m2)

The Hamilton Depression (HAM-D) Rating Score provides an indication of depression using 17 items rating symptoms from 0 (absent); 1 (mild); 2 (moderate); 3 (severe) to 4 (incapacitating)

- Rate of change (slope) per year from baseline to post baseline Visits V3, V7 and V11 with V11 being most important
- Responder analyses may be generated after review of initial results on changes from baseline described above.

For computation of rate of change (slope) each subject's value will be associated with number of days from Baseline when it was recorded. The rate of change (slope) per day will then be multiplied by 365.25 to be expressed as a rate of change (slope) per year to compare with published literature.

All participants performed CNS MRI (performed in 1.5T) at V-3 visit and at V11 (after the last infusion).

Select MRI Parameters analyzed will include from V-3 (Baseline for MRI) through V11:

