7.2.9. Evaluation of the CNS by magnetic resonance imaging of the brain

The test will be performed on an MRI machine. Conventional sequences will be obtained, used for the screening obtained before and after the use of paramagnetic contrast (gadolinium).

The sequences obtained will be submitted to a post-processing using the software FreeSurfer. This software is intended for the study of in vivo cortical and subcortical brain anatomy processed individually (evaluation of gray matter). The possibilities of FS are cortical surface reconstruction, cortical thickness calculation, cortical and subcortical structures segmentation, volumetric analysis, tractography analysis. Spreadsheets will be used to group individual data and generate a database.

[figure not shown]

Figure 10. Example of areas evaluated for average cortical thickness in the following regions of both hemispheres: prefrontal, lateral orbitofrontal, superior frontal and caudal anterior cingulate.

The sequence by DTI (*Diffusion Tensor Imaging*) will also be evaluated for the purpose of studying the pathways of the brain white matter. The magnetic resonance tractography technique evaluates nerve fibers through the traces of the diffusion of water represented by a tensor, with the union of points and forming the image of a nerve pathway; this technique of RM tractography does not demonstrate fiber to fiber, but rather a set of them, indicating possible nerve paths by the white substance. The clinical applicability of the tractography is to measure the diameter of brain nerve fibers and their density, the state of myelinization in neurogenesis, evaluation of the degree of (de)myelinization throughout age and in cases of disease (Figure 11 and 12).

[figure not shown]

Figure 11. Figure of brain MRI using the DTI (tractography) sequence.

[figure not shown]

Figure 12. Figure of MRI using DTI (tractography) sequence of the cerebellum, bulb, bridge, midbrain and brain.

For the execution of this study, it may be necessary, depending on the clinical condition of the participant and the clinical evaluation performed by the physician, the use of sedative, in which it will be defined at the time of the examination which will be used. This evaluation will be carried out in visits V-3 and V11.

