8.4. Measurement of secondary variables

Secondly, the safety as well as preliminary evidence of efficacy of the Cellavita-HD investigational product will be evaluated through of the following variables

a) Check for clinical neurological improvement throughout the study:

The UHDRS scale will be evaluated at each visit to measure neurological improvement.

b) Check the overall improvement in disease severity by the CIBIS scale throughout treatment:

The profile of the CIBIS scale will be considered for the evaluation of the overall clinical improvement of the participant through the treatments of the study.

c) BMI assessment:

BMI (Body Mass Index) will be evaluated through BMI profiles obtained during treatment.

d) Evaluate the suicide domain of the HAM-D scale throughout treatment:

It will be evaluated especially the domain "Suicide" by means of classification scores, in which scores of 8 – 13 correspond to mild depression, 14 – 18 to moderate, from 19 - 22 to severe and above 23 points to very severe depression. The "suicide" domain of the HAM-D scale will be evaluated through the profiles obtained throughout the treatment.

e) Neurological evaluation by magnetic resonance imaging of the brain:

It will be assessed through the profiles obtained during the treatment of the following measures:

- Cortical thickness measurements;
- Volumes of the various brain structures, especially the core of the base, with special attention to the caudate;
 - Identifiable metabolic changes in proton spectroscopy.

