Early termination visits will be allocated to the nearest scheduled visit where data was to be collected but is not recorded.

All analyses of changes, % changes, etc. will be by scheduled visits.

For analyses of abnormalities, data from both scheduled visits and unscheduled visits will be included.

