#### 7.4.2. Analysis on Secondary Efficacy Endpoint

Continuous secondary efficacy endpoints will be analyzed as indicated above for the primary efficacy endpoint.

Categorical efficacy data will be analyzed using a Fisher's exact test.

Responder analysis may be performed using thresholds for responders using logistic regression. Covariates for logistic regression will include baseline value of the dependent variable

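### MRI has one post-baseline scan per person, so the Treatment*Day model the SAP assigns to it cannot give a usable slope comparison; ANCOVA can

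*SAP*

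**What the plan says.** - **Scans.** Protocol 7.2.9: "This evaluation will be carried out in visits V-3 and V11". SAP 4.1.2 confirms two scans per person: "All participants performed CNS MRI (performed in 1.5T) at V-3 visit and at V11 (after the last infusion". V-3 is named as the MRI baseline ("Select MRI Parameters analyzed will include from V-3 (Baseline for MRI) through V11"). This agrees with the general rule in SAP 4.1.1 and 7.1, since no later pre-dose scan is planned.
- **Clock.** SAP 4.1.2: "For computation of rate of change (slope) each subject's value will be associated with number of days from Baseline when it was recorded". The daily rate is then multiplied by 365.25. For MRI the clock therefore starts at V-3, while treatment starts at V0 (SAP section 3).
- **Model.** SAP 7.4.2: "Continuous secondary efficacy endpoints will be analyzed as indicated above for the primary efficacy endpoint". SAP 7.4.1 gives that model as an MMRM with Treatment, Baseline and Treatment*Day and an unstructured covariance matrix. It adds that the model may be changed because of the small sample and COVID-19 visit timing.
- **Scope.** SAP 4.1.2 lists 12 gray-matter and 24 white-matter parameters, 36 in all. It gives no separate model for them.
- **Protocol description.** Protocol 8.4 says of imaging: "It will be assessed through the profiles obtained during the treatment of the following measures". Only one of the two scans falls after treatment has begun.

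**The concern.** The primary model was written for TMS, which is scored at every visit. For TMS, Treatment*Day compares slopes built from many values per person. For MRI the same rule leaves a single post-baseline value once the V-3 scan is used as the covariate. There are then no repeated measures, the unstructured matrix reduces to one variance, and the slope term has no within-person information.

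At stake is the whole imaging objective, including the caudate, which the protocol singles out. A literal programmer would produce estimates too imprecise to use. A less literal one would have to choose another model after seeing the data.

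The second matter is meaning. SAP 4.1.2 annualises slopes so that they can be set beside published figures. The MRI rate would span run-in plus treatment, whereas the TMS slope normally starts at V0. The two are different quantities.

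**Working it through.** **1. The plan's own interval.** Protocol 4.4 gives at most 90 days before treatment and 330 days after: 90 + 330 = 420, the stated total. The windows in Protocol 4.5 allow more: 37 (V-3 to V-2) + 37 (V-2 to V-1) + 30 (V-1 to V0) = 104 days, so 434 in total, or 439 with V11 at +5. The 90 and the 104 do not agree.

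**2. Can Treatment*Day be estimated?** Take 28 pooled active and 7 placebo participants, the V11 value as response and the V-3 value as covariate. That gives 35 records. The design columns are intercept, treatment, baseline, day in active and day in placebo. If everyone is scanned on the same day, both day columns are combinations of intercept and treatment. The rank is 3 of 5, so there is no estimate.

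**3. If scan days differ.** Assume a residual SD of 1 for V11 given V-3.
- Two-point rate: SE = sqrt(1/28 + 1/7) / (420/365.25) = 0.4226 / 1.150 = 0.37 per year.
- Treatment*Day: SE is roughly sqrt(1/27 + 1/6) / (SD of scan day in years) = 0.451 / SD.
- Run-in assumed uniform over 31 to 104 days and V11 over 0 to 5 days late: SD = sqrt(73²/12 + 5²/12) = 21.1 days = 0.058 years. This gives about 7.8; the exact median over simulated designs is 8.1. Ratio 8.1/0.37 = 22.
- V11 assumed up to 120 days late: SD = sqrt(73²/12 + 120²/12) = 40.5 days = 0.111 years. This gives about 4.1; exact median 4.3. Ratio 4.3/0.37 = 12.

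**4. Simulation with an effect.** None of the inputs is in the documents; all are assumed: decline 4% per year, effect 3% per year from V0, between-person rate SD 2% per year, scan noise SD 1.5%, baseline SD 12%, run-in 31 to 104 days, with and without added V11 delay.

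| Analysis | SE (% per year) | Power |
|---|---|---|
| Treatment*Day, one record each | 16 to 27 | about 5% |
| Two-point rate or V11 ANCOVA | 1.2 to 1.4 | 53 to 57% |

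With no true effect, every method rejects in about 5% of runs.

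**5. Other readings of the SAP.** With the V-3 scan entered as a day-0 response there are 70 records, the design has full rank and the slope difference is estimable. With Day as a visit category there is only one post-baseline level, so the model is an ANCOVA at V11 and gives no slope.

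**6. The V-3 clock.** If the effect acts fully from V0 for T = 330 days after a run-in of R days, the annualised arm difference is multiplied by T/(R + T).

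| R (days) | Factor |
|---|---|
| 31 | 330/361 = 0.91 |
| 60 | 330/390 = 0.85 |
| 90 | 330/420 = 0.79 |
| 104 | 330/434 = 0.76 |

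The 31-day case takes V-2 the day after V-3, V-1 30 days later and V0 on the same day as V-1. A shorter run-in brings the factor nearer to 1. A near-constant divisor scales estimate and SE together, so the test is essentially unchanged: in the simulation the V-3 rate gave 2.5 with SE 1.2, and ANCOVA per treated year gave 3.0 with SE 1.4. Both ratios are about 2.1.

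**The case against.** The strongest reply is that SAP 4.1.2 already describes a workable quantity. Two scans give each person an exact two-point rate, and comparing those rates is efficient. The SAP never says what the response rows are, and it allows the model to be changed. V-3 as baseline is the only pre-dose scan available, so it is not a poor choice.

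Much of this stands. It would be wrong to say that two scans hold no within-person rate; what they lack is a check on linearity. But SAP 7.4.2 points to a model in which baseline is a covariate, nothing selects a two-point or day-0 reading for MRI, and the clause on changing the model names no alternative.

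A reader might infer three stronger points, which the documents do not support:
- **That the run-in would cause a real effect to be missed.** It precedes randomisation and is common to all arms. It rescales the difference and leaves power and type I error essentially unchanged. Nor does the SAP call the run-in treatment time.
- **That scan timing would create false effects.** Rejection under no effect stays near 5%. The Treatment*Day result is uninformative, not biased toward a finding.
- **That early-termination scans would be passed off as V11.** Protocol 7.4 asks for V11 procedures at a closing visit, and SAP 7.1 says "Early termination visits will be allocated to the nearest scheduled visit where data was to be collected but is not recorded". But SAP 4.1.2 states that all participants were scanned at V11, and for slopes "each subject's value will be associated with number of days from Baseline when it was recorded", which keeps the true day.

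**Conclusion.** The concern holds for the model. Applied to MRI as it is to TMS, the rule yields either no Treatment*Day estimate or one with a standard error more than ten times that of a two-point rate or ANCOVA. The rank result needs only equal scan days. The size of the ratio rests on the assumed spread of scan days, and the power figures on the assumed effect and variances.

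The V-3 clock is a lesser point about interpretation. An effect acting fully from V0 would be reported at 0.79 of its annual size at the stated 90-day run-in, and at 0.76 to 0.91 over run-ins of 104 to 31 days.

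This is a secondary endpoint and the data themselves are adequate. The change should be made, but it does not threaten the trial.

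**What to change.** 1. In SAP 4.1.2 and 7.4.2, take the MRI parameters out of the Treatment*Day model. Analyse the V11 value, or the change from V-3 to V11, by ANCOVA with treatment and the V-3 value as terms.
2. Report the days from V-3 to V0 and from V0 to V11 by arm.
3. If an annual figure is given, either state that a V-3 to V11 rate includes the untreated run-in, or divide the arm difference in change by the V0 to V11 time. The second option assumes that change during the run-in is equal across arms on average, which randomisation at V0 supports.
4. Reconcile the 90-day maximum in Protocol 4.4 with the 104 days that the windows in Protocol 4.5 allow.

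The cost is a few sentences of SAP text and a simpler model. No new scans are needed. The SE per treated year is larger than that of the V-3 rate (1.4 against 1.2 in the simulation), in step with the larger estimate, so nothing is lost in power.
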